## **11 Study duration, Premature Termination of the Study**

### **11.1 Study Duration**

Start of the trial:

Date of randomization of first patient

Planned end of recruitment	6,5 months (LPFV, last patient first visit)
Last Patient Last Visit:	3 months (LPLV, last patient last visit)
Planned duration of single patient participation:	90 days

## 11.2 Definition of the End of the Study

The study will end at the last visit of the last patient.

## 11.3 Premature Study Termination

### 11.3.1 Premature Termination of Study Participation of a Single Patient

A patient is free to withdraw consent and discontinue participation in the study at any time, without prejudice to further treatment according to standard clinical practice. In this case the patient will be asked to permit the conduct of the study termination visit (cf. section 9.3). In certain circumstances the investigator may exclude a patient from further study participation irrespective of the patient's will. Reasons may be:

- treatment failure
- insufficient compliance
- further participation might jeopardize the patient's health or well-being
- termination of the entire study.

If, after treatment initiation, a patient's participation is realized not to agree with the inclusion and exclusion criteria, the principal investigator will decide on further participation.

In case of premature termination, the reason will be recorded on the CRF.

### 11.3.2 Premature Termination of the Entire Study

The sponsor may terminate the entire study for relevant medical or administrative reasons. Reasons for termination will be documented in detail. If, in the view of an investigator, there are ethical issues or any other issues contradicting study continuation, the principle investigator must immediately be informed. Particular reasons for termination of the study may be:

- insufficient recruitment
- serious problems with the quality of the study data which cannot be solved
- discovery of an unexpected, serious or unacceptable risk to patients enrolled in the study
- new scientific evidence suggesting that study continuation is not justified.

## 12 Statistical Considerations

The randomized groups will be descriptively compared on all baseline variables using summary statistics such as mean and standard deviation, median and quartiles, or frequency and percent, as appropriate. In inferential statistical analyses two-sided significance tests will be applied with a local significance level alpha=0.05. All point estimates of parameters of

interest will be supplemented by 95% confidence intervals unless otherwise stated. SAS or SPSS statistical software will be used for all data analyses.

#### Description of the primary efficacy / test accuracy analysis and population

The primary efficacy analysis will include all randomized subjects (full analysis set) and will be performed according to the intent-to-treat principle, i.e. all subjects are analyzed in the group to which they were randomized. Additional sensitivity analyses will be performed according to the per-protocol principle. The effect of AT-II versus control on the biomarker [TIMP-2]\*[IGFBP7] will be estimated with a non-parametric 90% confidence interval of the location shift between the distributions of the biomarker [TIMP-2]\*[IGFBP7] in the AT-II and the control group, respectively.

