Number of Patients/ Sample size:	Expected [TIMP-2]*[IGFBP7] level in the control group: median=0.84, Q1=0.35, Q3=1.57 and in the AT-II group: median=0.58, Q1=0.26, Q3=1.20 (based on Meersch et al., Intensive Care Med 2017). A total number of 64 patients will be recruited and a number of 32 patients will be randomized to each of the two treatment arms. With an expected 5% dropout rate, up to 2 patients per treatment arm will be non-evaluable. With a number of n=30 evaluable patients per treatment arm, the location shift between the distributions of the biomarker [TIMP-2]*[IGFBP7] in the AT-II and the control group can be

	estimated with an expected precision $\pm 0.35\text{ng/ml}^2/1000$ (half-width of the 95% confidence interval).
Inclusion Criteria:	
Inclusion criteria for registration
 
 
1. Adult patients scheduled for cardiac surgery with cardiopulmonary bypass (CPB),
 
2. 18 years of age or older,
 
3. cardiac index <math>> 2.1 \text{ l/min per square meter}</math>,
 
4. Written informed consent.
 
 
Inclusion criteria for randomization
 
Registered patients will be randomized only if
 
 
1. <math>\Delta</math>-renin (difference between post- and pre-operation) <math>\geq 3.7 \mu\text{U/ml}</math> 4h after CPB.
 
2. postoperative hypotension requiring vasopressors
 

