	
significance level alpha=0.05. All point estimates of parameters of interest will be supplemented by 95% confidence intervals unless otherwise stated. SAS or SPSS statistical software will be used for all data analyses.
 
Description of the primary efficacy / test accuracy analysis and population:
 
The primary efficacy analysis will include all randomized subjects (full analysis set) and will be performed according to the intention-to-treat principle, i.e. all subjects are analyzed in the group to which they were randomized. Additional sensitivity analyses will be performed according to the per-protocol principle. The effect of AT-II versus placebo on the biomarker [TIMP-2]*[IGFBP7] will be estimated with a non-parametric 95% confidence interval of the location shift between the distributions of the biomarker [TIMP-2]*[IGFBP7] in the AT-II and the placebo group, respectively.
 
Safety:
 
Safety data will be evaluated descriptively, including all recruited study patients who received at least one dose of study therapy (safety population). Results are reported by mean parameter estimates and associated 95% confidence intervals.
 
Secondary endpoints:
 
Statistical analysis of the pre-specified secondary endpoints will be performed with descriptive and inferential statistical methods.

Financial Support:	The project is supported by the DFG
Schedule	
Planned start date of the study (FPFV): 01.10.2021      Planned end date of recruitment (LPFV): 15.04.2022      Planned end date of the study (LPLV): 15.07.2022
 
Planned recruitment duration: 6,5 months      Duration of single patient participation: 90 days      Planned overall duration of the study: 9,5 months

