## 3.2 Endpoints

### 3.2.1 Primary Endpoint

The primary study endpoint is

- **Difference between [TIMP-2]\*[IGFBP7] levels 12h after randomization and [TIMP-2]\*[IGFBP7] levels at randomization.**

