#### Sample size

The expected median [TIMP-2]\*[IGFBP7] level in the control group is median control=0.84 (Q1=0.35, Q3=1.57) and in the AT-II group median AT-II=0.58 (Q1=0.26, Q3=1.20), based on Meersch et al., Intensive Care Med 2017. A total number of 64 patients will be recruited and a number of 32 patients will be randomized to each of the two treatment arms. With an expected 5% dropout rate, up to 2 patients per treatment arm will be non-evaluable. With a number of n=30 evaluable patients per treatment arm, the location shift between the distributions of the biomarker [TIMP-2]\*[IGFBP7] in the AT-II and the control group can be estimated with an expected precision  $\pm 0.285\text{ng/ml}^2/1000$  (half-width of the 90% confidence interval).

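### The primary analysis has two confidence levels: 95% (half-width 0.35) in the synopsis and 90% (half-width 0.285) in Section 12

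*Protocol*

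**What the plan says.** Four current places in the protocol fix the confidence level of the primary interval, and they fall into two pairs.

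- Synopsis, Statistical Methods: the effect "will be estimated with a non-parametric 95% confidence interval of the location shift". Synopsis, Number of Patients/Sample size: expected precision ±0.35 (ng/ml)²/1000, described as the "half-width of the 95% confidence interval".
- Section 12, primary efficacy analysis: the effect "will be estimated with a non-parametric 90% confidence interval of the location shift". Section 12, Sample size: expected precision ±0.285 in the same unit, described as the "half-width of the 90% confidence interval".

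Everything else in the planning is common to both: control median 0.84 (quartiles 0.35 and 1.57), AT-II median 0.58 (quartiles 0.26 and 1.20), 5% dropout, 30 evaluable and 32 randomized per arm, 64 in total.

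The opening of Section 12 says that "two-sided significance tests will be applied with a local significance level alpha=0.05" and that estimates of "interest will be supplemented by 95% confidence intervals unless otherwise stated". The synopsis hypothesis is superiority. Section 4 calls the study a feasibility trial and also says what will follow if it is positive. No significance test is named for the primary endpoint.

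**The concern.** The protocol gives two complete specifications of its single primary analysis, and a reader cannot tell which one governs. The 95% default at the start of Section 12 does not settle it: it gives way where another level is stated, and the primary-analysis paragraph of Section 12 states 90%. That makes Section 12 consistent with itself but leaves it in conflict with the synopsis. A separate SAP could choose a level, but either choice would contradict part of the protocol.

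Two things are at stake. Whatever the interval is for, the reported limits and the planned precision differ. And since no primary test is named, the interval is the only primary inference described. If excluding zero is what makes the trial positive, the error rate depends on the section followed, and the protocol alone does not prevent the level from being chosen after the data are seen.

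**Working it through.** **Inputs.** Quartiles 0.35/0.84/1.57 (control) and 0.26/0.58/1.20 (AT-II), n = 30 evaluable per arm, 5% dropout; all from Section 12, Sample size, and the same in the synopsis. The protocol names no distribution, so several were fitted.

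**1. Sample size.** 30/0.95 = 31.6, so 32 per arm and 64 in total. This reproduces and does not depend on the confidence level.

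**2. Ratio of the stated half-widths.** 0.35/0.285 = 1.228. For a normal approximation the ratio would be 1.960/1.645 = 1.19. Rescaling by that ratio, 0.285 at 90% becomes 0.285 × 1.1916 = 0.340 at 95%, and 0.35 at 95% becomes 0.35/1.1916 = 0.294 at 90%. The two figures are close to one calculation at two levels.

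**3. Interval limits.** The Hodges-Lehmann interval takes order statistics of the 30 × 30 = 900 pairwise differences. The Mann-Whitney variance is 900 × 61/12 = 4575, with square root 67.6. The lower rank is near 450 − 1.960 × 67.6 = 317.4 at 95% and 450 − 1.645 × 67.6 = 338.7 at 90%. The ranks used are 318 and 583 (exact coverage 95.04%) and 339 and 562 (exact coverage 90.05%).

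**4. Half-widths on biomarker levels.** 20,000 simulated trials per fit:

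| Fit to the stated quartiles | Half-width 95% / 90% | Ratio | Zero excluded 95% / 90% | Levels disagree |
|---|---|---|---|---|
| Protocol's own figures | 0.35 / 0.285 | 1.228 | – | – |
| Log-normal, least squares on the quartiles | 0.349 / 0.286 | 1.222 | 21.0% / 31.3% | 10.2% |
| Log-normal, fitted on the log scale | 0.364 / 0.297 | 1.225 | 17.3% / 27.1% | 9.7% |
| Split log-normal, all quartiles exact | 0.367 / 0.302 | 1.215 | 16.3% / 25.9% | 9.6% |
| Weibull | 0.365 / 0.301 | 1.211 | 19.2% / 28.9% | 9.7% |

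The least-squares log-normal comes within 0.001 of both protocol figures, so neither is shown to be miscalculated. Other choices widen the range. A log-normal anchored on the medians gives 0.387/0.317, with zero excluded in 22.4% and 33.4% and disagreement in 11.0% (8,000 runs). A normal fit gives 0.426/0.356, ratio 1.197. A zero-truncated normal gives 0.330/0.276.

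**5. No treatment effect.** From the exact coverages, zero is excluded in 1 − 0.9504 = 5.0% of trials at 95% and 1 − 0.9005 = 10.0% at 90%, whatever the distribution.

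**6. Endpoint scale.** Section 3.2.1 defines the endpoint as the difference between "levels 12h after randomization and" those at randomization. The planning uses levels, and the protocol gives no spread for the change. As an assumption, take the least-squares log-normal at 12 h and a common log-normal baseline equal to the control distribution or to half of it:

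| Log-scale correlation | Baseline = control: 95% / 90% (disagree) | Baseline = half: 95% / 90% (disagree) |
|---|---|---|
| 0 | 0.710 / 0.587 (7.1%) | 0.520 / 0.429 (8.3%) |
| 0.5 | 0.494 / 0.406 (8.9%) | 0.373 / 0.307 (10.4%) |
| 0.9 | 0.227 / 0.187 (12.6%) | 0.205 / 0.168 (11.9%) |

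The ratio stays at 1.21 to 1.22, so the conflict is as large on the change scale. The half-width itself is not pinned down there.

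**The case against.** The best reply is that this is an estimation study. Both versions say the effect will be estimated, the sample size rests on precision with no power calculation, the 0.05 level is tied to significance tests of which none is named for the primary endpoint, and Section 4 speaks of a feasibility trial. On that reading only the reported limits move. This stands as a limit on the consequence: the error rates and exclusion rates count only if excluding zero decides success. It does not remove the contradiction, and the superiority hypothesis and the reference to a positive trial keep the other reading open.

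An SAP not seen here may fix the level before unblinding, so a choice made after seeing the data is a possibility, not an established fault. That is fair, but the protocol would still contradict itself.

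The four fits in the first table also give too narrow a picture. Across all the fits tried, half-widths run from about 0.33 to 0.43 at 95% and 0.28 to 0.36 at 90%, and the 95% interval is about 20 to 23% wider. The disagreement of roughly 10% holds up on the biomarker levels.

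Finally, planning on levels rather than on the change is a separate weakness from the choice of confidence level. That is right. It is noted because aligning the level would not by itself make either half-width the precision of the primary endpoint.

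**Conclusion.** The concern holds: the confidence level of the primary interval is contradictory as written, and no rule in the protocol resolves it. Without further assumptions, the plan yields two different intervals and two stated precisions, 0.35 and 0.285, for one design. The point estimate and the sample size are the same under both.

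If excluding zero is the success criterion, the false-positive rate is 5% or 10% depending on the section. Under the planned quartiles the chance of excluding zero is about 16 to 22% at 95% and 26 to 33% at 90% for the log-normal and Weibull fits, and the two sections would disagree in about 10% of trials (7 to 13% under the assumed change-score scenarios). These rates depend on the assumed distributions; the 5% and 10% do not. The calculations cannot show which level was intended.

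**What to change.** Before unblinding, state one confidence level with its matching half-width identically in the two synopsis rows (sample size and statistical methods) and the two Section 12 paragraphs (primary analysis and sample size). Add one sentence saying whether the interval decides if the trial is positive or serves estimation only.

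- **95% with 0.35.** This is the level that matches the stated two-sided alpha of 0.05 if the interval decides. Change the two Section 12 paragraphs. The cost is that the precision stated there widens from 0.285 to 0.35 and, if excluding zero decides, the chance of doing so is the lower of the two ranges above.
- **90% with 0.285.** Change the two synopsis rows, and declare either a two-sided 10% (one-sided 5%) criterion or estimation only. If excluding zero decides, the cost is a two-sided false-positive rate of 10% instead of 5%.

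On either route, state that the half-width was derived from biomarker levels and not from the 12 h minus randomization change that defines the endpoint. Only wording changes; the sample size stays at 64.

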	
randomization and [TIMP-2]*[IGFBP7] levels at randomization
 
Secondary Endpoints:
 
 
• occurrence of AKI within 72h after cardiac surgery (according to the KDIGO criteria)
 
• occurrence of moderate and severe AKI within 72h after cardiac surgery (according to the KDIGO stage 2 and 3)
 
• amount of volume application
 
• transient (<72h) and persistent (<72h) AKI
 
• fluid status
 
• dose and duration of vasopressor use
 
• creatinine clearance on day one after cardiac surgery
 
• free-days through day 28 of vasoactive medications and mechanical ventilation
 
• renal recovery at day 90 (renal recovery is defined as serum creatinine levels < 0.5 mg/dl higher than baseline serum creatinine (creatinine level before surgery)
 
• 30-day, 60-day and 90-day mortality
 
• length of ICU stay
 
• length of hospital stay
 
• use and duration of renal replacement therapy within hospital stay
 
• use of RRT at days 30, 60, 90
 
• MAKE90 (major adverse kidney events consisting of mortality, dialysis dependency, persistent renal dysfunction (defined as serum creatinine <math>\geq</math> 2x compared to baseline value) at day 90
 
• Effect of ACEi/ARBs use on the AT II effect
 
• Correlation between the severity of hyperreninemia and the AT II effect
 
 
Other variables:
 
 
• Surveillance of vital parameters on ICU
 
• Safety laboratory parameters
 
• Occurrence of thromboembolism
 
• Adverse events
 
 
Add-on study:
 
 
• determination of further biomarkers (e.g. KIM-1, chitinase, NGAL, hyaluronic acid) and anti- and pro-inflammatory mediators (IL-6, IL-10...)
 

Planned Number of Study Centers:	1

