### 5.2.3 Distribution of Gender in the Study Population

We expect a gender distribution of (male: female) 70:30. No patient will be excluded from the study on the basis of gender. Gender will be used for covariate adjustment in the final analysis. A subgroup analysis will be performed according to gender.

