#### Multivariable statistical analyses

Multivariable statistical analyses will be applied in order to identify independent prognostic factors of clinical outcomes. The identified prognostic factors will allow determining risk groups of patients with expected outcomes of different severity. Survival data will be analyzed using multivariable Cox proportional hazards models after checking the proportional hazards assumption based on the Schoenfeld residuals. Binary outcomes will be analyzed by multivariable logistic regression. Model building will be performed using stepwise variable selection based on Akaike's information criterion (AIC) in order to identify relevant and meaningful independent variables of a respective outcome. Models will be fitted and model parameters will be estimated using Maximum Likelihood methods. The final models will be validated using cross-validation techniques.

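### The primary comparison uses the biomarker value at randomisation at most by subtraction; a baseline-adjusted analysis on a scale suited to skewed data would probably be more precise, by an amount the protocol does not let one fix

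*Protocol*

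**What the plan says.** - **Endpoint.** Protocol 3.2.1 defines the primary endpoint as a difference between "levels 12h after randomization and" those at randomisation. The synopsis (1.1) agrees: "randomization and [TIMP-2]*[IGFBP7] levels at randomization".
- **Primary analysis.** Section 12 says the effect of AT-II "will be estimated with a non-parametric 90% confidence interval of the location shift between the distributions of the biomarker". The synopsis names the same method at another level: "will be estimated with a non-parametric 95% confidence interval of the location shift". Neither names a covariate, and both refer to the biomarker rather than its change.
- **Measurement.** The flow chart (1.2) and visit T3 in 9.2 schedule the urinary biomarker at randomisation and at 12 h.
- **Sample size.** Section 12 justifies 30 evaluable patients per arm only by an expected half-width, ±0.285 at 90% (synopsis: ±0.35 at 95%). The inputs are quartiles of biomarker levels, not changes.
- **Gender.** Section 5.2.3 states: "Gender will be used for covariate adjustment in the final analysis". The multivariable paragraph of Section 12 has another purpose: "Multivariable statistical analyses will be applied in order to identify independent prognostic factors of clinical outcomes". It covers survival data and binary outcomes ("Binary outcomes will be analyzed by multivariable logistic regression") and chooses variables by AIC ("Model building will be performed using stepwise variable selection based on Akaike's information criterion (AIC").

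**The concern.** When width is the only design criterion, the analysis should use the information already collected that bears on width. The obvious candidate is each patient's own value at randomisation. Subtracting it amounts to fixing the slope of the 12-h value on baseline at 1. If the true slope is lower, the change carries the noise of two measurements, and the estimate moves with any chance difference between arms at baseline. If the analysis sentence is taken literally and levels are compared, baseline is not used at all.

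At stake is precision in a trial of 64 patients whose result is meant to support a follow-up trial. The gender sentence is a smaller, separate matter: it announces an adjustment for which Section 12 gives no method when the outcome is metric.

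**Working it through.** **1. The plan's own figures.** Patients: 30/(1 − 0.05) = 31.6, so 32 per arm and 64 in total; this reproduces. Half-width: SD = IQR/1.349 gives (1.57 − 0.35)/1.349 = 0.904 for control and (1.20 − 0.26)/1.349 = 0.697 for AT-II. Then 1.645 × √(0.904²/30 + 0.697²/30) = 0.343 at 90%, and 0.409 at 95%. Simulated Hodges-Lehmann intervals give 0.321/0.392 for lognormal and 0.304/0.368 for gamma shapes. A piecewise-uniform shape through the quartiles, capped near 2.5 in controls, gives 0.286/0.343. The stated 0.285/0.35 therefore depends on an unstated shape and is not shown to be wrong. It is a precision for levels.

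**2. Change score against adjustment, equal SDs.** Let ρ be the baseline/12-h correlation (not in the protocol; assumed). Relative to a level, the variance of a change is 2(1 − ρ) and that of a baseline-adjusted value is 1 − ρ². The half-width ratio, adjusted to change, is √((1 + ρ)/2). The equivalent number per arm under a change score is 30 × 2/(1 + ρ).

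| ρ | ratio | narrower by | equivalent n per arm |
|---|---|---|---|
| 0.3 | 0.806 | 19% | 46 |
| 0.5 | 0.866 | 13% | 40 |
| 0.7 | 0.922 | 8% | 35 |
| 0.9 | 0.975 | 2.5% | 32 |

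The stated ±0.285 carries over to a change only at ρ = 0.5, where 2(1 − ρ) = 1. At ρ = 0.3 it becomes 0.285 × √1.4 = 0.337.

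**3. Unequal SDs.** With k = SD(baseline)/SD(12 h), the ratio is √((1 − ρ²)/(1 + k² − 2ρk)). For k = 0.5, ρ = 0.5 it is √(0.75/0.75) = 1: the slope ρ/k is 1 and nothing is gained. For k = 1.5, ρ = 0.5 it is √(0.75/1.75) = 0.655.

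**4. Simulation on skewed data.** Lognormal values, 30 per arm, 2000 trials per scenario. From the protocol: log-SD at 12 h = ln(1.57/0.35)/1.349 = 1.11, and ratio 0.58/0.84 = 0.69. Assumed: baseline median 0.6, and baseline log-SD either equal to or half the 12-h value. Chance of two-sided p<0.05:

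| Baseline log-SD | ρ | Mann-Whitney, raw change | ANCOVA on logs | Quade |
|---|---|---|---|---|
| equal | 0.3 | 19% | 26% | 25% |
| equal | 0.5 | 21% | 31% | 29% |
| equal | 0.7 | 32% | 43% | 37% |
| half | 0.3 | 23% | 28% | 26% |
| half | 0.5 | 25% | 29% | 27% |
| half | 0.7 | 36% | 42% | 38% |

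The gains run from 2 points (27 − 25) to 11 points (43 − 32). Type I error was about 4 to 5%. Linear ANCOVA on raw values reached only 16 to 24%. Simulation error is about √(0.25 × 0.75/2000) = 1 point, so the smallest gains are barely distinguishable from none. With assumed baseline medians of 0.3 and 0.84 also tried, the smallest margin for Quade was 25.0% against 25.3%.

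**5. Chance imbalance.** The SD of the between-arm difference in mean log baseline is 1.11 × √(2/30) = 0.29. With equal spreads, an imbalance of that size moves the unadjusted shift by about 0.13, 0.09 and 0.04 at ρ = 0.3, 0.5 and 0.7. The planned difference in medians is 0.84 − 0.58 = 0.26.

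**6. Gender.** Allowing for one degree of freedom, the half-width factor is √((1 − R²) × (58/57) × (1 + 1/57)). It falls below 1 only if gender explains more than about 3.4% of the variance. At R² = 5% it is 0.992, a gain of about 1%.

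**The case against.** The planned comparison is valid. A non-parametric shift of the change is protected by randomisation, already uses baseline in one way, and matches the absolute difference in 3.2.1. A reader might call it biased; that holds only conditional on a given chance imbalance. Over randomisations the estimate is unbiased.

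A reader might also infer that a change score is efficient only when the two values are almost perfectly correlated. That assumes equal SDs; what matters is whether the slope is near 1, and the protocol gives nothing from which to judge it. Nor does adjustment always help: linear adjustment of raw skewed values gave no gain in power, and in a rank-based interval the ratio reached 1.07, that is 7% wider, when baseline had half the scale.

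The simulated gains mix two changes, adjustment and scale. In the half-spread, ρ = 0.5 scenario the log slope is 0.5/0.5 = 1, so the four-point gain of log ANCOVA there reflects scale. Lognormal data also suit the log model. Against that, Quade uses no logs and still gained 5 to 8 points with equal spreads.

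A log ratio is a different effect measure from the one in 3.2.1 and from the unit of the stated precision. This stands, and the fix must deal with it.

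On gender, 5.2.3 speaks of the final analysis, not the primary one, so it does not contradict the unadjusted primary method. A rank-based shift could also be stratified by a binary factor.

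The details of an adjusted model may be in an analysis plan that is not shown. That does not answer the main point: the protocol is not silent but fixes an unadjusted primary estimator.

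**Conclusion.** The point holds as a recommendation for a better primary method, not as an error that invalidates the trial. The protocol fixes an unadjusted location shift although a baseline value is scheduled for every randomised patient and precision is its only sample-size criterion.

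The likely gain is modest to useful: about 2.5% to 19% of the half-width for ρ from 0.9 to 0.3 with equal SDs on the analysis scale, and about 2 to 11 points in the chance of p<0.05 under the lognormal assumptions above. It is nil against a change score on the same scale when the slope is near 1. The correlation, baseline median and baseline spread are all assumptions, so the documents do not support saying that the trial loses a known amount of precision. They support saying that it probably loses some, and that avoiding this costs almost nothing.

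The gender sentence is a minor consistency gap: an announced adjustment with no method for a metric outcome, and a selection procedure that would not guarantee that gender stays in a model. It is not a source of precision at this sample size.

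**What to change.** In Section 12 and the synopsis, replace the primary-analysis sentence with a short paragraph that:

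1. makes the primary comparison baseline-adjusted on a scale suited to skewed data: either ANCOVA of the log 12-h value on the log value at randomisation, reported as a ratio with its confidence interval, or Quade's rank ANCOVA for the test;
2. keeps the non-parametric location shift in (ng/ml)²/1000 with its interval, so that an estimate matching the stated endpoint and precision is still reported;
3. states that this shift is computed on the change from randomisation, so that 3.2.1 and Section 12 agree. Adjustment does not settle this by itself, because change and level give the same effect only when both are on the same scale as the covariate, and a raw change is not a log change;
4. enters gender in the same model and reads the gender subgroup as a treatment-by-gender term, so that 5.2.3 can be carried out, or else says to which analysis 5.2.3 applies.

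The cost is one paragraph in two places, with no new patients, samples or measurements. The downside should be stated openly: under the log model the main effect is a ratio, and the stated precision then applies only to the supportive raw-scale shift. The 90% level in Section 12 and the 95% level in the synopsis are a separate discrepancy, to be settled in the same edit.
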